each treatment	of patients that participate in the extension study. Approximate
	possible ranges provided.

Page 3 of 84

Patients entering extension trial from Part 1 of trial 1407-0030 (Fasted) double blind treatment period until Week 12: • 25 mg (0 to 40 patients) • 50 mg (0 to 80 patients) • 100 mg (0 to 80 patients) • 200 mg (40 to 100 patients) • placebo (0 to 20 patients) (Fasted) open label treatment period: • 100 mg (80 to 140 patients) • 200 mg (60 to 100 patients)
Patients entering extension trial from Part 2 of trial 1407-0030
(Fed) open label treatment period:400 mg (0 to 90 patients)
Patients with moderate-to-severe plaque psoriasis who have
completed treatment in the preceding trial
 Have completed treatment in the preceding trial without early discontinuation, agree to continue treatment in 1407-0005, and for patients entering from Part 1 of trial 1407-0030 ≥PASI50 response upon completing the trial 1407-0030 Week 24 end-of-treatment visit for patients entering from Part 2 of trial 1407-0030 ≥PASI50 response upon completing the trial 1407-0030 Week 12 end-of-treatment visit or perceived patient improvement, at the discretion of the Investigator. Women of childbearing potential (WOCBP) must be ready to use highly effective methods of birth control Have not developed any of the exclusion criteria of the preceding trial, including relevant chronic or acute infections Must agree to continue to avoid intake of any restricted medication No plan to receive a live vaccination during trial conduct Must agree to continue to adhere to the rules of UV-light protection No ongoing AEs related to trial medication (including gastric intolerance) from 1407-0030
BI 730357
25 mg, 50 mg, 100 mg, 200 mg, 400 mg BI 730357 per day
Oral (p.o.)

Boehringer Ingelheim BI Trial No.: 1407-0005

c22181693-04

Comparator product(s)	Placebo to BI 730357 (for patients entering from Part 1 of trial
	1407-0030, 12 week double blind period only)
dose	Not applicable
method and route of administration	p.o.
Duration of treatment	Approximately 6 years
Statistical methods	Descriptive statistics include exposure adjusted rate of patients
	reporting a TEAE, responder analysis, and time to loss of response.

Proprietary confidential information © 2020 Boehringer Ingelheim International GmbH or one or more of its affiliated companies

FLOW CHART

Trial Periods	Screening/ Double Blind Treatment							(Open La	abel Tr	eatment	t						

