3. DESCRIPTION OF DESIGN AND TRIAL POPULATION

OVERALL TRIAL DESIGN AND PLAN 3.1

Trial 1407-0005 is a multicentre, long-term extension trial in patients who have completed Phase II PoC/dose-ranging trial 1407-0030 with demonstrated improvement in disease severity and acceptable safety and tolerability of trial drug, as described below. The trial is designed to evaluate long-term safety and efficacy of BI 730357 in patients with moderate-tosevere plaque PsO.

Two groups of patients are to be entered into this trial, including up to (approximately) 180 patients entered in the original trial 1407-0030 protocol (now Part 1) and up to (approximately) 90 patients entered in an extended dose-ranging segment, now Part 2 of the amended trial 1407-0030 protocol. Actual numbers of subjects entering the extension trial are to be determined by response in the preceding study and the number of patients that participate in the extension study.

In the first group (Part 1), patients will be considered eligible to participate in this long-term extension trial upon completing the trial 1407-0030 Week 24 end-of-treatment visit with a \geq PASI50 response. BI 730357 dose levels of up to 200 mg *q.d.* are to be administered under fasting conditions to patients in this group, reflecting the dose levels evaluated during Part 1 of trial 1407-0030.

- Patients entering the extension trial will remain on their blinded BI 730357 dose treatment from the preceding trial until the open label period of 1407-0005 begins at Visit 2/Week 12.
- At Visit 2/Week 12, patients presently assigned to double blind treatment of placebo, 25 mg, 50 mg, and 100 mg will be reassigned to the 100 mg open label dose, and patients presently assigned to the double blind treatment of 200 mg will be reassigned to 200 mg open label dose. Refer to Figure 3.1: 1.

In the second patient group (Part 2), patients will be considered eligible to participate in this trial upon completing the trial 1407-0030 Week 12 end-of-treatment visit with a ≥PASI50 response or perceived patient improvement, at the discretion of the Investigator. Patients are to be considered eligible only if also without ongoing AEs consistent with intolerance of trial medication (including gastric intolerance) that in the opinion of the investigator would compromise the safety of the patient.

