7. STATISTICAL METHODS AND DETERMINATION OF SAMPLE SIZE

7.1 STATISTICAL DESIGN - MODEL

This is an extension trial of patients with moderate to severe chronic plaque psoriasis treated with BI 730357 after participation in preceding Trial 1407-0030. Descriptive statistics include exposure adjusted rate of patients reporting a TEAE, responder analysis (e.g., achievement of PASI75, sPGA of clear or almost clear, etc.), and time to loss of response (e.g. achievement of PASI75, sPGA of clear or almost clear, etc.).

This trial is designed to gain as much exposure as possible with adequate documentation of safety, efficacy, and tolerability.

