7.2 NULL AND ALTERNATIVE HYPOTHESES

There is no formal statistical hypothesis testing in this trial.

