7.7 DETERMINATION OF SAMPLE SIZE

The sample size will be up to approximately 270 patients. It will be determined by patients who have completed the randomized treatment period without early treatment discontinuation in 1407-0030 and are willing and able to continue treatment in this extension trial. Patients in the subsequent Psoriasis trials are expected to enroll in this extension trial, if applicable.

Page 60 of 84

8. INFORMED CONSENT, TRIAL RECORDS, DATA PROTECTION, PUBLICATION POLICY, AND ADMINISTRATIVE STRUCTURE

The trial will be carried out in compliance with the protocol, the ethical principles laid down in the Declaration of Helsinki, in accordance with the ICH Harmonized Guideline for Good Clinical Practice (GCP), relevant BI Standard Operating Procedures (SOPs), the EU regulation 536/2014 and other relevant regulations. Investigators and site staff must adhere to these principles.

Standard medical care (prophylactic, diagnostic and therapeutic procedures) remains the responsibility of the treating physician of the patient.

The investigator will inform the sponsor immediately of any urgent safety measures taken to protect the trial patients against any immediate hazard, as well as of any serious breaches of the protocol or of ICH GCP.

The Boehringer Ingelheim transparency and publication policy can be found on the following web page: trials.boehringer-ingelheim.com. The rights of the investigator and of the sponsor with regard to publication of the results of this trial are described in the investigator contract. As a rule, no trial results should be published prior to finalization of the Clinical Trial Report.

The certificate of insurance cover is made available to the investigator and the patients, and is stored in the ISF.

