5. ENDPOINTS(S)

5.1 PRIMARY ENDPOINT(S)

The primary endpoint is the occurrence of treatment emergent adverse events (TEAEs) up to Week 288.

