- If AE onset date \leq date of End of Treatment visit in the preceding trial (1407-0030) < AE worsening date < date of first intake after week 12 re-assignment, then the AE is assigned to “first 12 weeks of treatment”.

If an AE worsening occurs on the day of week 12 visit, actual time between AE onset and study medication taken will be compared to determine AE time period (first 12 weeks, second treatment period).

If the subject discontinues before the day of week 12 visit, date of first intake after week 12 re-assignment will be missing, the AE worsening will still be assigned to “first 12 weeks of treatment”.

- If date of first intake after week 12 re-assignment \leq AE worsening date \leq date of last intake + 7 days, then the AE is assigned to “second treatment period”.

For patients who rolled over from Part 1 of the 1407-0030 trial if the onset date of an AE occurs prior to Week 12 and continues beyond Week 12 with a worsening RCTC grade after Week 12 then the AE will be captured as a TEAE both during the first 12-week period of 1407-0005 (as a new-onset TEAE) and during the second treatment period (beyond Week 12, as a worsening-TEAE).

Because there is no scheduled titration for patients who rolled over from Part 2 of trial 1407-0030 adverse events will only be summarized for the entire treatment period and will not be summarized for the first 12 weeks and after 12 weeks for these patients.

Due to differing doses, differing titration schedules and different timeframe for entering this study between patients from part 1 and part 2 of trial 1407_00030, several sets of adverse event analyses, each consisting of 11 summaries, will be presented:

- Events up to 12 weeks for patients who rolled over from Part 1 of trial 1407_00030 with treatment columns BI 25 mg, BI 50 mg, BI 100 mg and BI 200 mg
- Events after 12 weeks for patients who rolled over from Part 1 of trial 1407_00030

with treatment columns BI 25 mg/BI 100 mg, BI 50 mg/BI 100 mg, BI 100 mg/BI 100 mg and BI 200 mg/ BI 200mg.

- All events for patients who rolled over from Part 2 of trial 1407-0030 with treatment column BI 400 mg
- All events from all patients who rolled over from trial 1407-0030 (part 1 and part 2 combined) where events are classified under the treatment at onset in 1407-0005 with treatment columns BI 25 mg, BI 50 mg, BI 100 mg, BI 200 mg and BI 400 mg

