Patients from part 1 of trial 1407_00030 who discontinue study treatment prior to Week 12 will be excluded from the second and fourth sets of analyses above. Due to varying length of exposure to the various doses, exposure adjusted incidence rates will be presented in addition to number and percentage of patients with events in the fifth set above (classification by dose at onset).

For the analysis of other safety data (laboratory data, vital signs ,suicidal ideation) summaries will be presented for the entire study, for the first 12 weeks of the study and after 12 weeks on study. For these outputs data from patients who rolled over from Part 1 and Part 2 of study 1407-0030 will be combined. In some of these data displays each treatment appears on a separate page. If deemed appropriate, additional displays showing descriptive statistics with figures for selected outcomes will be presented.

For efficacy summaries of response at Week 24 all patients from Part 1 of trial 1407-0030 will have data will be grouped as follows:

- 100 mg patients from part 1 of trial 1407-0030
 - 25 mg/100mg
 - 50 mg/100 mg
 - 100 mg/100mg
- 200 mg patients from part 1 of trial 1407-0030
- All patients from part 1 of trial 1407-0030
- 400 mg patients from part 2 of trial 1407-0030
- All patients from part 1 and part 2 of trial 1407-0030 combined

For efficacy summaries of time to loss of response data will be grouped as follows:

- 100 mg patients from part 1 of trial 1407-0030 (combing 25 mg/100mg, 50 mg/100 mg and 100 mg/100mg)
- 200 mg patients from part 1 of trial 1407-0030
- 400 mg patients from part 2 of trial 1407-0030

Efficacy response at Week 12 and 36 for patients from Part 2 of trial 1407-0030 will be summarized.

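### No listed adverse-event set has an all-BI 730357 column, and conflicting set numbers could drop early discontinuers from the only all-patient display

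*SAP*

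**What the plan says.** SAP 5.1: "The primary endpoint is the occurrence of treatment emergent adverse events (TEAEs) up to Week 288". SAP 7.4.1 and Protocol 7.3.4 analyse it as an exposure-adjusted incidence rate per treatment group with an exact 95% interval.

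SAP 6.1 lists four adverse-event sets:

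1. Part 1 patients up to Week 12, by blinded dose.
2. Part 1 patients after Week 12, by dose sequence (such as 25 mg then 100 mg).
3. Part 2 patients, 400 mg only.
4. All events in all patients of both parts, by dose at onset, "with treatment columns BI 25 mg, BI 50 mg, BI 100 mg, BI 200 mg and BI 400 mg".

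The same section then excludes Part 1 patients who stop before Week 12 from the second and fourth sets. It assigns exposure-adjusted rates to a fifth set, identified as the dose-at-onset classification.

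For Week 24 efficacy, SAP 6.1 plans an all-Part-1 group and a group labelled "All patients from part 1 and part 2 of trial 1407-0030 combined". Protocol 7.1 gives the purpose of the design: "This trial is designed to gain as much exposure as possible".

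**The concern.** The trial exists to accumulate exposure and describe long-term safety, yet the listed adverse-event displays split that exposure and never add it up. The secondary Week 24 endpoints get an all-patient group and the primary safety endpoint does not. The loss falls mainly on uncommon events such as malignancy, MACE, opportunistic infection and hepatic injury, where a single dose column may show no case or one case with a wide interval.

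The set numbering matters separately. If early Part 1 discontinuers are removed from the combined set, the only all-patient display omits patients whose early stopping may itself be related to tolerability.

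**Working it through.** **Total sample size.** The parts are about 180 and about 90: 180 + 90 = 270, which agrees with Protocol 7.7 ("The sample size will be up to approximately 270 patients"). The documents give no precision target, expected person-years or retention to reproduce.

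**Inputs.** The synopsis ranges are 80 to 140 patients on open-label 100 mg, 60 to 100 on open-label 200 mg, and up to 90 on 400 mg. Week 288 is 2016 days, and 2016/365.25 = 5.52 years. The first 12 weeks are 84/365.25 = 0.23 years, leaving 5.29 years open-label.

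**Person-years (PY) at full follow-up.**
- All patients: 270 × 5.52 = 1490
- All Part 1: 180 × 5.52 = 994
- 400 mg: 90 × 5.52 = 497
- 100 mg, open-label time only: 80 × 5.29 = 423 to 140 × 5.29 = 741
- 200 mg: 60 × 5.29 + 40 × 0.23 = 327 to 100 × 5.52 = 552

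**Formula.** With zero events the two-sided exact 95% Poisson upper limit is −ln(0.025)/PY = 3.689/PY. Results per 100 PY, with mean follow-up as a fraction of plan:

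| Column | 100% | 50% | 25% |
|---|---|---|---|
| All patients | 0.25 | 0.50 | 0.99 |
| All Part 1 | 0.37 | 0.74 | 1.49 |
| 100 mg | 0.50 to 0.87 | 1.00 to 1.74 | 1.99 to 3.49 |
| 200 mg | 0.67 to 1.13 | 1.34 to 2.26 | 2.67 to 4.52 |
| 400 mg | 0.74 | 1.49 | 2.97 |

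The ratio of a dose limit to the pooled limit is total PY over column PY: 1490/741 = 2.0 at the least and 1490/327 = 4.6 at the most. It does not change with retention if retention is equal across columns. The extremes are taken one at a time; 140 and 60 together would exceed 180.

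A mid-range case with 110, 70 and 90 patients and a mean of 2 years gives 220, 140 and 180 PY, 540 in all. The limits are 1.68, 2.63 and 2.05 by dose against 0.68 pooled.

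The 25 and 50 mg columns hold at most 12 weeks per patient. For 40 and 80 patients that is 9.2 and 18.4 PY, with zero-event limits of 40 and 20 per 100 PY.

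The pooled figure slightly overstates active exposure. Up to 20 patients may take placebo for 12 weeks, which is 20 × 0.23 = 4.6 PY.

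**Can the columns be added?** Not for common events. SAP 6.1 itself counts an event that worsens after Week 12 in both periods, and a patient who changes dose can appear in more than one dose column. As an illustration, suppose 40% have a TEAE before Week 12 and 70% after, independently. The counts sum to 110%, while 1 − 0.6 × 0.3 = 82% have at least one. For very rare events, adding columns is a fair approximation but not a planned output. SAP 7.4.1 also runs time at risk from study drug start without giving a start date for each dose.

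**Set numbers.** If the fourth set is the fourth one listed, the exclusion applies to the combined display and contradicts Protocol 7.3.4. If the dose-at-onset set is the fifth, the fourth set is missing from the list. The two statements cannot both fit a four-item list.

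**The case against.** The primary rate is defined per treatment group in both documents, and no pooled estimate is promised. SAP 6.1 gives reasons for separate sets: different doses, titration schedules and entry times. A pooled rate would mix 25 to 400 mg, fasted and fed dosing, and cohorts with different entry criteria. This stands. It is a reason to show a total beside the dose columns, not to make it the primary estimate.

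A reader might infer that Part 1 has no whole-extension view. The documents do not support that. The combined set covers all events, and Part 2 patients are assigned only 400 mg, so its 25 to 200 mg columns show Part 1 throughout the extension, split by dose at onset. Only a single Part 1 column is absent.

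A reader might also infer that no overall estimate exists anywhere in the plan. The reference to a fifth set suggests the list is incomplete. An omitted set containing Part 1 patients would fit the exclusion rule, but its content is not stated, so it can be neither credited with a total nor assumed to lack one.

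Nor is it right that a total can never be rebuilt. With zero events nobody is double counted, SAP 7.7 plans exposure by actual treatment, and individual values are listed. The reader would still have to construct the rate and its interval. Finally, a total column does not make a case more likely to be seen, since any case already appears under some dose. It improves the estimate and its limits.

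**Conclusion.** The point holds as an inexpensive improvement plus a numbering conflict that needs resolving. No listed adverse-event set pools BI 730357 exposure, and per-dose zero-event limits are about 2 to 4.6 times the pooled limit. That ratio rests on the synopsis patient numbers, 270 patients in total and equal retention across columns. The absolute limits depend on retention, which the documents do not give. The ratio ignores optional up-titration from 100 to 200 mg, which would move person-time between those columns.

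It does not follow that the primary endpoint goes unestimated, since the planned rates by dose at onset are an estimate under the protocol's definition. No error rate or power is affected: "There is no formal statistical hypothesis testing in this trial".

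**What to change.** In SAP 6.1:

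1. Make the list of sets agree with the later references to the second, fourth and fifth sets, adding any omitted set. State that Part 1 patients who stop before Week 12 remain in the combined set.
2. Add an All BI 730357 column to the combined set, with number, percentage, exposure-adjusted rate and exact 95% CI. Count each patient once, from first BI 730357 intake in 1407-0005 to first event, or to last dose + 7 days (or death or last contact if earlier, as in SAP 7.4.1). Exclude placebo time.
3. Add an All Part 1 column on the same basis.
4. State that both columns supplement the dose columns and leave the per-treatment-group primary analysis unchanged.

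The cost is SAP wording and two columns in tables already planned; no new data are needed. As supplementary columns they leave the protocol's definition of the primary rate as it is. The small downside is that the pooled rate averages over doses, fed and fasted dosing and entry cohorts, so a footnote should say that it must be read with the dose columns.

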Patients in the 1407-0030 trial that fulfil the criteria for rollover will be asked to participate in this extension trial. Upon their agreement, they will immediately enter the treatment phase. Therefore, no screening period is defined in this trial.

* Within the On-treatment period, it can be divided into Period 1 (first 12 weeks) and Period 2 (after 12 weeks) for patients from part 1 of the 1407-0030 trial.

For the main safety analyses, Adverse Events (AEs) for patients who rolled over from Part 1 of trial 1407-0030 will be classified to one of the following time periods: “first 12 weeks of treatment”, “second treatment period”, or “follow up”. Section 7.3.4 of the protocol specifies that, all AEs and laboratory assessments with an onset between start of treatment and end of the residual effect period (REP), a period of 7 days after the last dose of trial medication for this trial, will be assigned to the “on-treatment” period for evaluation.

Detailed rules for assigning AEs to these time periods based on the onset dates of the AEs for patients who rolled over from Part 1 of the 1407-0030 trial are listed below (such AEs will be classified as new-onset TEAEs):

- If date of Start of Treatment visit in trial (1407-0005) \leq AE onset date $<$ date of first intake after week 12 re-assignment, then the AE is assigned to “first 12 weeks of treatment”.

If an AE occurs on the day of week 12 visit, actual time between AE onset and study medication taken will be compared to determine AE time period (first 12 weeks, second treatment period).

If the subject discontinues before the day of week 12 visit, date of first intake after week 12 re-assignment will be missing, the AE will still be assigned to “first 12 weeks of treatment”.

- If date of first intake after week 12 re-assignment \leq AE onset date \leq date of last intake + 7 days, then the AE is assigned to “second treatment period”.

Section 7.3.4 of the protocol specifies that adverse events that start before first drug intake and deteriorate under treatment will also be considered as ‘treatment emergent’. Worsening will be determined by a more severe grade according to Rheumatology Common Toxicity Criteria (RCTC) Version 2.0 Detailed rules for assigning such AEs of patients from Part 1 of the 1407-0030 trial to these time periods based on the onset dates and worsening dates of the AEs are listed below (such AEs such be classified as worsening-severity TEAEs):

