7. PLANNED ANALYSIS

The format of the listings and tables will follow the standards defined in the BI corporate guideline “Reporting of clinical trials and project summaries” .

The individual values of all patients will be listed, sorted by treatment, patient number and visit. The listings will be included in Appendix 16.2 of the CTR.

For EoT tables, the set of summary statistics is: N / Mean / SD / Min / Median / Max.

For appendix tables, the set of summary statistics is: N / Mean / SD / Min / Q1 (lower quartile) / Median / Q3 (upper quartile) / Max.

Tabulations of frequencies for categorical data will include all possible categories and will display the number of observations in a category as well as the percentage (%) relative to the respective treatment group. Percentages will be rounded to one decimal place. The category “missing” will be displayed only if there are actually missing values. Percentages will be based on all patients in the respective patient set no matter whether they have non-missing values or not.

No interim analysis is planned for this trial.

For patients from Part 1 of the 1407-0030 trial planned treatment for first 12 weeks of treatment is defined as treatment patient received at the end of 1407-0030. Planned treatment for after 12 weeks (Period 2) is defined as the treatment patient assigned from IVRS at week 12 visit (V2). For patients who titrate according to the protocol from 100 g *q.d.* dose to 200 g *q.d.* dose, if the investigator determines that the patient may benefit from the higher dose, 200 g *q.d.* dose will be the planned dose after the titration.

Subject data listings of data used in the analyses (i.e. demographic and baseline characteristics and key efficacy endpoints) will also be provided and included in Appendix 16.2 of the CTR.

Disposition of the patient population participating in the trial will be summarised by presentation of the frequency of patients screened, entered, screened but not entered, treated, entered but not treated. Within treated patients, data for patients rolled over from Part 1 of trial 1407-00030 will be summarized by treatment periods (period 1 - first 12 weeks of treatment and period 2 – open label treatment after week 12) for treatment ongoing patients, patients complete planned treatment period and patients who are prematurely discontinued, by reason.

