7.8.1 Adverse Events

The analyses of adverse events will be descriptive in nature. All analyses of AEs will be based on the number of patients with AEs (not the number of AEs).

Unless otherwise specified, the analyses of AEs will be descriptive in nature. All analyses of AEs will be based on the number of subjects with AEs and NOT on the number of AEs.

The analysis of AEs will be based on the concept of treatment emergent AEs. That means that all AEs occurring between first drug intake till 7 days after last drug intake will be assigned to the received treatment. All AEs occurring before first drug intake will be assigned to 'screening' and all AEs occurring after last drug intake + 7 days will be assigned to 'follow-up' (for listings only). For details on the treatment definition, see [Section 6.1](#).

According to ICH E3 [\(5\)](#), in addition to Deaths and serious adverse events, 'other significant' AEs need to be listed in the clinical trial report. These will be any non-serious adverse event that led to an action taken with study drug (e.g. discontinuation or dose reduced or interrupted). An overall summary of adverse events will be presented.

The frequency of subjects with AEs will be summarised by treatment, primary system organ class and PT using the version of MedDRA at the database lock. Separate tables will be provided for subjects with SAEs, AEs leading to treatment discontinuation and related AEs.

The system organ classes will be sorted by default by decreasing frequency and PTs will be sorted by decreasing frequency within SOC.

For further details on summarization of AE data, please refer to the guideline 'Handling and summarization of adverse event data for clinical trial reports and integrated summaries' [\(4\)](#).

The severity of AEs will be summarised by the maximum intensity of the events each patient had (as indicated by the recorded RCTC version 2 grade). This will show the number and percent of patients who had at most mild, moderate, severe, and life threatening events. Severe adverse event is defined as an AE with RCTC grade equals to 3 (severe) or 4 (life threatening).

Groupings of adverse events and adverse events of special interest (AESI)

The AESI have been defined in the protocol.

Other user-defined special adverse event grouped term for BI 730357 specified in the following [Table 7.8.1:1](#).

Table 7.8.1: 1 User Defined Adverse Event Group Terms

N	Term	Definition #

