1	SMQ Drug Related Hepatic Disorders	SMQ Drug related hepatic disorders – comprehensive search (20000006)
2	SMQ Opportunistic infections	MedDRA SMQ Opportunistic Infections (narrow)
3	Tuberculosis related terms	BIcMQ “Tuberculosis related terms” BIcMQ (30000107)(broad)
4	Severe infections	SOC “Infections and infestations” with eCRF severity grade >= Rheumatology Common Toxicity Criteria (RCTC) Grade 3
5	Gastritis related terms	
 BIcMQ Gastritis (broad) [32008061]

This column indicates whether the Term(s) provided in the second column are MedDRA preferred terms (PT), Standardised MedDRA Queries (SMQ) or BI customised MedDRA Queries (BIcMQ).

In addition, adjudicated MACE (provided by [REDACTED] will be summarized by indication, treatment, primary system organ class and preferred term.

The user defined AE categories will be updated accordingly with Safety SAP updates.

The following periods will be defined for assessing adverse events for patients from Part 1 of the 1407-0030 trial.:

- First 12 weeks of treatment
- Second treatment period

For patients from Part 1 of the 1407-0030 trial, AEs with onset date on day of week 12 visit, the AE onset time will be compared with first drug administration time of the dose dispensed at the Week 12 visit to determine AE period. The treatment label for second period will be a combination of actual treatment in first 12 weeks of treatment and second period treatment.

Additionally an analysis including patients from both parts of the 1407-0030 trial will be performed in which adverse events are classified under the dose the patient was receiving at the onset of the TEAE.

AE summaries

An overall summary of adverse events will be presented. The frequency of patients with adverse events will be summarized by treatment, primary system organ class and preferred term according to MedDRA. Separate tables will be provided for patients with:

- Drug-related AEs
- AESIs

- AEs leading to discontinuation
- Serious AEs
- Other significant AEs
- AE by worst RCTC intensity
- Investigator defined drug-related serious AEs
- User defined AE categories

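### SAP 6.1 lists four adverse event analysis sets but refers to a fourth and a fifth in ways that cannot both be right, so it is unclear whether Part 1 early stoppers belong in the combined dose-at-onset set

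*SAP*

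**What the plan says.** SAP 6.1 announces "several sets of adverse event analyses, each consisting of 11 summaries, will be presented" and gives four bullets:

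1. Part 1 patients, events up to Week 12, by dose.
2. Part 1 patients, events after Week 12, by dose sequence.
3. Part 2 patients, all events, 400 mg.
4. Both parts: "All events from all patients who rolled over from trial 1407-0030 (part 1 and part 2 combined) where events are classified" by treatment at onset, with columns from 25 mg to 400 mg.

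The next paragraph says that Part 1 patients "who discontinue study treatment prior to Week 12 will be excluded from the second and fourth sets of analyses above". It then promises exposure-adjusted incidence rates, besides counts and percentages, "in the fifth set above (classification by dose at onset").

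SAP 7.8.1 describes the combined analysis again without an exclusion: "Additionally an analysis including patients from both parts of the 1407-0030 trial will be performed in which adverse events are classified under the dose" being received at onset. SAP 6.3 and 7.8 put adverse event analyses on the Treated Set, and protocol 7.3.4 includes all treated patients in the safety analysis. SAP 7.4.1 defines the primary analysis as an exposure-adjusted TEAE rate. It names none of the four sets and states no exclusion.

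**The concern.** The two ordinals decide who is counted in a safety table. If a programmer applies the exclusion by list position, treated Part 1 patients who stopped before Week 12 drop out of the combined set, with their events and their person-time. Within 6.1 this is the only set for which exposure-adjusted rates are promised.

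The loss would not be neutral. The 25 mg and 50 mg doses end at Week 12, when those patients are reassigned to 100 mg. Under the positional reading, an adverse event that makes such a patient stop before Week 12 could therefore never appear in the 25 mg or 50 mg column of the combined set. SAP 7.8.1 plans the output most exposed to this: "Separate tables will be provided for subjects with SAEs, AEs leading to treatment discontinuation and related AEs".

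The events would not vanish from the report. SAP 6.1 covers these patients ("If the subject discontinues before the day of week 12 visit, date of first intake after week 12 re-assignment will be missing") and assigns their events to the first 12-week period. Set 1 would show them as counts and percentages, but 6.1 promises no rate there.

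**Working it through.** **Matching the ordinals to the list.** Four sets are listed, and the highest ordinal cited is the fifth.

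| Reading | *Fourth* is | *Fifth* is | Result |
|---|---|---|---|
| List position | Both parts, dose at onset | Not listed | Early stoppers leave a set described as covering all patients; the rates are placed in a set that does not exist |
| Descriptive label | Not identifiable | Both parts, dose at onset | Everyone stays in the combined set; the exclusion points to an undefined set |
| Second bullet, whose text is broken, counted as two | Part 2 only | Both parts, dose at onset | Excluding Part 1 patients from a Part 2 set does nothing |

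No count makes both references meaningful.

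**Illustration of size.** The plan has no figure of its own to reproduce. Inputs from the documents: 25 mg group of 0 to 40 patients (protocol synopsis), taken at its cap of 40; 12 weeks = 84 days. Assumed: *k* early stoppers, a mean of 42 days on drug, and one third to two thirds of them stopping for an adverse event. The 7-day residual effect period is ignored.

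Person-years with everyone included = [(40 − *k*) × 84 + *k* × 42] / 365.25. Events leading to discontinuation = *k*/3 to 2*k*/3. Rate = 100 × events / person-years.

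| *k* | Person-years | Events, all included | Rate per 100 PY, all included | Events shown if excluded |
|---|---|---|---|---|
| 0 | 9.20 | 0 | 0 | 0 |
| 1 | 9.08 | 0.33–0.67 | 3.7–7.3 | 0 |
| 2 | 8.97 | 0.67–1.33 | 7.4–14.9 | 0 |
| 4 | 8.74 | 1.33–2.67 | 15.3–30.5 | 0 |

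Moving the mean stop to 3 or 9 weeks shifts the lower end for *k* = 2 to 7.3–7.5 and the upper end for *k* = 4 to 29.7–31.3. If discontinuation for an adverse event instead had a constant rate of 2 to 3 per 100 PY (also assumed), the expected number is 9.20 × 0.02 to 9.20 × 0.03 = 0.18 to 0.28 events.

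The column is small. With 0 events, the exact Poisson 95% upper limit is 3.689 / person-years of those remaining. For *k* = 2 that is 3.689 / (38 × 84 / 365.25) = 3.689 / 8.74 = 42.2 per 100 PY. For *k* = 4 it is 3.689 / (36 × 84 / 365.25) = 3.689 / 8.28 = 44.6 per 100 PY.

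**Direction for adverse events in general.** Take the same 40 patients with other assumptions: 30% of completers have an event, at week 6 on average; 15% stop early; stoppers with an event have it at week 3 on average; the other stoppers contribute 7 weeks.

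- Stoppers excluded: 34 × 0.3 = 10.2 events in 34 × (0.3 × 6 + 0.7 × 12) = 346.8 weeks = 6.65 PY, or 153.5 per 100 PY.
- Included, 80% of the 6 stoppers with an event: 15.0 events in 346.8 + 6 × (0.8 × 3 + 0.2 × 7) = 369.6 weeks = 7.08 PY, or 211.8.
- Included, no stopper with an event: 10.2 events in 346.8 + 6 × 7 = 388.8 weeks = 7.45 PY, or 136.9.

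The exclusion can therefore move an overall rate either way. For events leading to discontinuation before Week 12 it can only remove events.

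**The case against.** The best counter-argument is that this is a stale cross-reference that a careful reader can resolve. The fifth set carries a descriptive label that fits only one listed set, and neighbouring sentences use *fourth* and *fifth* as if for different sets. The bullet itself, SAP 6.3, 7.8 and 7.8.1, and protocol 7.3.4 all point to including everyone. SAP 7.4.1 separately provides exposure-adjusted rates with exact confidence intervals and no exclusion. Set 1 keeps the early events, and the trial tests no hypothesis.

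SAP 6.1 also says that all Part 1 patients had been in the study for more than 12 weeks when the first Part 2 patient enrolled on 10 December 2020. Taken literally, that could mean there are no early stoppers and no effect, although the SAP still carries rules for such patients.

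Most of this stands. The inclusive reading is the better supported one, no distortion of the primary rate is shown, and the size depends on assumptions. What does not follow is that the text can be left alone. The exclusion is an explicit instruction, and in the list as printed the fourth set is the combined one. A bullet lost when the text was read from PDF cannot be fully ruled out, but nothing visible suggests it.

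**Conclusion.** The concern holds. SAP 6.1 is internally inconsistent on the population of one safety analysis set, and one literal reading removes treated patients from a set that other parts of the SAP and the protocol say should contain them. That much needs no assumption.

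The consequence cannot be sized from the documents. It is nil if nobody in Part 1 stopped before Week 12, or if the set is programmed by its label. Under the positional reading and the assumed 2 to 4 early stoppers, the 25 mg column would show 0 events leading to discontinuation instead of 0.7 to 2.7 (7.4 to 30.5 per 100 PY). These figures all lie within the uncertainty of so small a column. No whole-trial figure is claimed. The point should be corrected before programming; it does not call the primary analysis into question.

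**What to change.** In SAP 6.1:

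- Replace the ordinals with set names.
- Limit the early-stopper exclusion to the Part 1 after-Week-12 set.
- Assign the exposure-adjusted rates to the dose-at-onset set by name.

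In 6.1 and 7.4.1, state that the dose-at-onset set and the primary rate include every Treated Set patient, with early stoppers contributing events and person-time under the dose they took. If exclusion from the combined set is really intended, justify it and declare it in SAP section 4, which at present reports no changes to the planned analysis.

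Report how many Part 1 patients stopped before Week 12, by dose. SAP section 7 already says "data for patients rolled over from Part 1 of trial 1407-00030 will be summarized by treatment periods" and by reason, and its general rules express frequencies relative to treatment group, so this needs at most a sentence confirming the split by dose.

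The cost is a few words of SAP text and, at most, a split of a table already planned. No new data are needed.
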